## Statistical analysis plan

### Data Management.

All study data and tracking will be entered into an research electronic data system, REDCap ([www.REDCap.org](http://www.REDCap.org)), a secure research electronic data management system with validated data entry, audit trails for tracking data manipulation and export procedures. It is HIPAA complaint satisfying all local, state, and federal regulation for the capture and storage of private health information for research purposes.

### Power

We aimed to enroll at least 60 mothers (30 mothers per arm), with planned over recruitment to account for up to 20% loss to follow-up (i.e., 72 infants) during the pilot trial. Because we did not have reliable estimates for the confidence intervals, standard errors, or mean differences for our outcomes a priori, our sample size was based on Whitehead's recommendations to have at least 20 persons per treatment arm in a pilot trial when expecting a small standardized difference ( $\delta=0.2$ ) to achieve at least 80% in the main trial. Because our emphasis was on feasibility, this pilot trial was not powered to detect statistically significant changes in outcome and mediating variables between arms.

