## Randomization

Using STATA software, the Statistician will generate a random allocation sequence stratified by GA at birth (GA <28 weeks and >28 weeks) to balance representation of the youngest and sickest infants. We will use permuted block randomization for each stratum, with block sizes of 2, 4, and 6 and a 1:1 treatment allocation. The Statistician will upload the sequence into REDCap, have no contact with subjects, and will be independent of all assessment procedures. REDCap's secure randomization feature prevents the study team from viewing the treatment allocation sequence, ensuring allocation concealment. Research assistants will enroll and collect baseline data before randomization. The Principal Investigator (PI) / Clinical Research Coordinator (CRC) will randomize each family after baseline survey completion to minimize dropout effects on randomization.

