## Eligibility Criteria

### Inclusion Criteria:

- English-speaking parents
- Parents preterm infants born 25 0/7-31 6/7 weeks gestational age (GA)
- Parents who had a singleton or twin birth
- Parents 18 years of age or older

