### Analysis

REDCAP data will be exported to Stata 15 software, where we will analyze sources of missing data and calculate descriptive/summary statistics. We will graph trends for all variables over infant Day of Life (DOL) and CGA, comparing boxplots between arms and over time. We will compute means and 95% CIs for changes from baseline (T1 to T2-4) for each outcome by arm. At each follow-up (T2-4), we will compute mean differences and 95% CI between arms to evaluate trends in outcomes. Mothers with multiple births will have one infant randomly selected for analysis. We will not test for statistically significant differences between groups in outcome measures or estimate effect sizes in this pilot study, because the primary purpose is to determine feasibility of our procedures to inform the planning and design of a larger trial.

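### If 60 mothers is the number to be kept, the over-recruitment figure of 72 covers 16.7% loss, not 20%, and it is given in infants; separately, two actual enrolments are not reconciled

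*Combined protocol and SAP*

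**What the plan says.** All references are to the combined protocol and SAP.

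- **Power, base number:** "We aimed to enroll at least 60 mothers (30 mothers per arm").
- **Power, allowance for loss:** "planned over recruitment to account for up to 20% loss to follow-up (i.e., 72 infants) during the pilot trial".
- **Power, basis for the size:** a published pilot-trial recommendation of "at least 20 persons per treatment arm in a pilot trial".
- **Randomization:** the study team "will randomize each family after baseline survey completion", "with block sizes of 2, 4, and 6 and a 1:1 treatment allocation".
- **Inclusion Criteria:** "Parents who had a singleton or twin birth" are eligible.
- **Analysis:** "Mothers with multiple births will have one infant randomly selected for analysis". Also: "We will not test for statistically significant differences between groups in outcome measures".
- **Study Design:** two actual enrolments appear, one of 44, counted as participants, and one of 64, counted as mothers of very preterm infants.
- **Detailed Description:** the project has two aims, usability and acceptability work to refine the program, and then a pilot randomized trial.

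**The concern.** Three things in a short space do not fit together.

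First, recruiting extra mothers to allow for loss protects a number that is to remain at the end. That calls for dividing by the expected retention. The figure given is what comes from adding 20% to the base, which always falls short of the loss it is meant to cover.

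Second, the sentence begins in mothers and ends in infants. With twins eligible, families randomized and one infant per mother analysed, those are different counts unless 72 means one index infant per mother. The text does not say so.

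Third, and separately, the two actual enrolments each have a noun but no phase or stage. In a pilot whose purpose is feasibility, the number of mothers randomized is a main result, and a reader should not have to guess it.

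What is at stake is accurate reporting of the recruitment and retention plan, which a larger trial would draw on. The validity of a test is not at stake.

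**Working it through.** **Inputs.** Base 60 mothers, 30 per arm; loss up to 20%; stated over-recruitment figure 72; basis of 20 per arm (all from Power). Allocation 1:1 (Randomization).

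**1. Reproduce the stated figure.** Base × (1 + loss) = 60 × 1.20 = 72. This matches exactly.

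**2. What 72 delivers if 60 is to be kept, counting 72 as mothers.**
- Left after 20% loss: 72 × 0.80 = 57.6, or 57.6 / 2 = 28.8 per arm (about 58 and 29).
- Shortfall against 60: 60 − 57.6 = 2.4 mothers.
- Largest loss that still leaves 60: 1 − 60/72 = 16.7%.

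**3. What 20% protection of 60 needs.** Base / (1 − loss) = 60 / 0.80 = 75. By arm, 30 / 0.80 = 37.5, rounded up to 38, so 76 in total. Check: 76 × 0.80 = 60.8.

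**4. If 60 is only the enrolment aim.** No retained number is then stated, so the margin can be checked only against the basis of 20 per arm: 60 × 0.80 = 48, or 24 per arm.

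**5. Against the basis for the size.** Keeping 20 per arm (40 in all) after 20% loss needs 40 / 0.80 = 50 enrolled. Both 60 and 72 exceed this.

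**6. Unit.** Power counts mothers and then infants, Randomization allocates families, and Analysis uses one infant per mother. The number that governs precision is therefore mothers (one index infant each). Since 72 follows exactly from a count of mothers, it is most likely a count of mothers given the wrong noun.

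**7. Actual enrolments.** 64 − 44 = 20. Set against the aim of 60 mothers, 64 would meet it and 44 would not. No section assigns either figure to the usability phase, to the pilot trial, or to a stage such as enrolled, randomized or followed up.

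**The case against.** The best defence is that the text speaks of enrolling at least 60 and never names a retained target, so an inflation error is inferred and not stated. This stands in part, and is why the conclusion is conditional. It does not clear the sentence: over-recruitment on top of 60 to allow for loss points to 60 as the number to be kept, and if it is not, the 20% allowance protects no stated number.

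A second defence is that the consequence is close to nil. That stands. The gap is 2 to 3 mothers, the pilot is not powered for between-arm differences, and the basis of 20 per arm holds at the planned size.

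Three stronger readings are tempting, and the documents support none of them.

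- **That 72 counts every infant, twins included, so the margin could vanish.** If 12 of 60 mothers (20%) had twins, 72 infants would come from exactly 60 mothers and there would be no allowance at all. But the documents give no twin share, and on this reading the exact match with 60 × 1.20 would be a coincidence.
- **That the pilot is too small for its purpose.** The only stated basis is 20 per arm, which is met with room to spare at the planned size.
- **That 44 and 64 contradict each other, or that the recruitment aim was missed.** They carry different nouns and may belong to different phases or stages. The only figure expressed in mothers, 64, is above 60. What is missing is the statement of what each one counts.

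**Conclusion.** The point holds, and it is minor. On the natural reading that 60 mothers are to be kept, and with 72 counted in mothers, the stated size protects against 16.7% loss and not the 20% claimed; at 20% loss about 58 mothers (29 per arm) remain. If 60 is only an enrolment aim, the fault is instead a missing retained number. On either reading the unit should be mothers, and the sample-size basis is unaffected.

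The enrolment figures are a separate reporting matter. Two actual counts stand in one section without a phase or stage, and the documents do not allow them to be reconciled.

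**What to change.** In Power:

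- State that 60 mothers is the number to be kept or, if it is only the enrolment aim, give the retained number.
- Express 72 in mothers.
- If 60 is to be kept, restate the margin: 72 mothers allow for up to 16.7% loss while keeping 60, or leave about 29 per arm at 20% loss. If the claim of 20% protection for 30 per arm is to remain, the figure that supports it is 76 mothers, but nothing in the plan requires that claim.

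In Study Design, say which phase and stage 44 and 64 each refer to, and state one number of mothers randomized in the pilot trial.

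The cost is a few words. No additional mothers are needed and the analysis does not change. The only thing given up is the stated loss allowance, which falls from 20% to 16.7% if 60 is the number to be kept.

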### Analysis

REDCAP data will be exported to Stata 15 software, where we will analyze sources of missing data and calculate descriptive/summary statistics. We will graph trends for all variables over infant Day of Life (DOL) and CGA, comparing boxplots between arms and over time. We will compute means and 95% CIs for changes from baseline (T1 to T2-4) for each outcome by arm. At each follow-up (T2-4), we will compute mean differences and 95% CI between arms to evaluate trends in outcomes. Mothers with multiple births will have one infant randomly selected for analysis. We will not test for statistically significant differences between groups in outcome measures or estimate effect sizes in this pilot study, because the primary purpose is to determine feasibility of our procedures to inform the planning and design of a larger trial.

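### Raw visit-by-visit arm differences in PROMIS scores ignore baseline and GA stratum and carry no missing-data assumption: some precision is lost, and the T4 contrast is biased if loss differs by arm (minor)

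*Combined protocol and SAP*

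**What the plan says.** The between-arm analysis is one sentence in the SAP's Analysis section: "At each follow-up (T2-4), we will compute mean differences and 95% CI between arms to evaluate trends in outcomes". The same section plans mean changes from baseline with 95% CIs within each arm, and graphs over time. On missing data it states that "we will analyze sources of missing data and calculate descriptive/summary statistics". It names no analysis set, missing-data assumption, covariate or longitudinal model.

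The Power section foresees attrition, "with planned over recruitment to account for up to 20% loss to follow-up", and answers it with numbers alone. The Randomization section stratifies by gestational age, but that stratum does not reappear in the analysis. The Outcome Measures table gives the baseline-to-T4 change as the reported result for depression and anxiety.

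The plan limits its own ambition: "We will not test for statistically significant differences between groups in outcome measures or estimate effect sizes in this pilot study".

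**The concern.** A raw mean difference at a visit can use only the mothers measured at that visit. Two things follow.

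- **Precision.** Every randomised mother has a baseline score, because randomisation follows the baseline survey. Leaving that score out of the arm contrast makes the interval wider than the collected data require. The contrast also leaves out the randomisation stratum.
- **Conditional bias.** T4 is the last visit, about a month after the infant goes home. For a mother missing at T4, her T1 to T3 scores do not inform the T4 contrast. If more distressed mothers leave one arm more often than the other, the T4 difference favours the arm that lost them. Over-recruitment restores numbers but does not remove this, and studying the sources of missingness changes no estimate.

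At stake are arm differences and intervals that will inform a larger trial. The Power section says that no reliable prior estimates existed.

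**Working it through.** **Inputs from the documents.** "We aimed to enroll at least 60 mothers (30 mothers per arm"; up to 20% loss; 1:1 allocation; SD 10, which is the PROMIS standardisation SD and not a trial SD.

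**Assumptions, not in the documents.** Between-visit correlation ρ (equal at 0.5 or 0.7, or AR(1) at 0.7 or 0.8); loss by arm; odds of loss multiplied by e per 1 SD higher distress; no true arm difference.

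**1. The plan's own figure.** 60 × (1 + 0.20) = 72 reproduces the stated target (60 / 0.80 would give 75). The sentence counts these as infants; I take them as 72 mothers, 36 per arm. After 20% loss, 36 × 0.8 = 28.8 per arm have T4 data.

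**2. Precision at T4.**
- Raw: SE = 10 × √(2/28.8) = 2.64; half-width 1.96 × 2.64 = 5.2 points.
- Baseline-adjusted (ANCOVA): multiply by √(1 − ρ²). For ρ = 0.5, 2.64 × 0.866 = 2.28. For ρ = 0.7, 2.64 × 0.714 = 1.88.
- Also using T2 and T3 for mothers missing at T4: with R² = 3ρ²/(1 + 2ρ), the variance is 200 × [(R² − ρ²)/36 + (1 − R²)/28.8]. For ρ = 0.5, R² = 0.375 and SE = √5.03 = 2.24. For ρ = 0.7, R² = 0.6125 and SE = √3.37 = 1.84.

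Simulation (4000 replicates, 36 per arm) agrees: raw 2.55–2.64; ANCOVA 2.31–2.34 (ρ = 0.5) and 1.88–1.89 (ρ = 0.7); longitudinal 2.30–2.32 and 1.85. Nearly all the gain comes from baseline; T2 and T3 add about 0.01 to 0.04.

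**3. Bias at T4, loss driven by the observed T3 score** (large-sample simulation, points; sign ignored)

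| Loss by arm | Raw T4 difference | Change from baseline | Longitudinal estimate |
|---|---|---|---|
| 20% / 20%, same mechanism | about 0 | about 0 | about 0 |
| 25% / 15% | 0.4–0.6 | about 0 to 0.12 | about 0 |
| 30% / 10% | 0.8–1.3 | about 0 (equal ρ), 0.25–0.34 (AR(1)) | about 0 |

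With 20% loss in each arm but distress-related in one arm only, the raw bias under equal correlation is 0.9–1.1. Across the 30/10 and one-arm-only scenarios, the change score is biased by at most about 0.5.

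The change score fares better for a simple reason. Under equal correlation, T4 and T1 have the same regression on T3, so the expected change given T3 is zero. Under AR(1) the fraction (1 − ρ) of the raw bias remains: 1.13 × 0.3 = 0.34 and 1.28 × 0.2 = 0.26, in line with the simulated 0.34 and 0.25.

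**4. Loss driven by the unseen T4 score, 30/10 split.** The raw bias is about 1.6 points. A longitudinal model reduces it to 0.6–1.1 and does not remove it.

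**The case against.** The strongest defence is purpose. This is a feasibility pilot, not powered on outcomes, with no tests planned. Descriptive summaries and a look at why data are missing fit that aim, and a repeated-measures model is heavier machinery than a small sample needs. Much of this stands, and it sets the severity. It does not remove the point, because arm differences with intervals are still computed and are meant to guide a later trial.

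A reader might also infer four stronger things that the documents do not support.

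- *That the plan discards T1 to T3.* It analyses T2 and T3 at their own visits, uses T1 in every change score and graphs trends. Only the earlier scores of mothers missing at T4 go unused, and only in the T4 contrast. Available-case analysis is itself an inference from a plan that names no analysis set.
- *That the reported change to T4 is off by about a point.* The 0.8 to 1.3 belongs to the raw T4 difference.
- *That the bias is about half of an effect the pilot expects.* The 0.2 comes from a sizing rule, "at least 20 persons per treatment arm in a pilot trial when expecting a small standardized difference", tied to power in the main trial. It is not a target for this pilot.
- *That the SE gain comes from recovering mothers lost at T4.* Almost all of it is baseline adjustment.

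The documents give no loss by arm, so differential loss is possible, not shown. The sentence on mean differences could also be read as differences in change. The SE would then be 2.64 × √(2(1 − ρ)), that is 2.64 at ρ = 0.5 and 2.04 at ρ = 0.7, still above ANCOVA.

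**Conclusion.** The point holds as a minor one. As written, the arm contrasts are raw, use only mothers measured at each visit, and omit baseline and GA stratum.

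The firmer cost is precision: an SE of about 2.6 where about 2.3 (ρ = 0.5) or 1.9 (ρ = 0.7) is available from data already collected. This rests on 36 per arm, 20% loss at T4, SD 10 and the assumed correlations. The effect of omitting the stratum is not quantified, since nothing in the documents relates GA to PROMIS scores.

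The bias is conditional: about 0.8 to 1.3 points in the raw T4 difference under the assumed 30% against 10% loss, or distress-related loss in one arm only; about 0 under the same loss in both arms; and 0 to 0.5 in the change from baseline. Each is small beside a half-width of about 5 points. The Study Design section gives actual enrolment as both 44 and 64. After 20% loss these leave 17.6 or 25.6 per arm and half-widths of 6.6 or 5.5, so the bias would weigh still less.

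**What to change.** For PROMIS depression and anxiety:

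- Keep the planned raw summaries and label them available-case.
- Add one repeated-measures estimate over T2 to T4 with arm, visit, arm-by-visit, baseline score and GA stratum. Report the arm difference and 95% CI at each visit, with no tests.
- If the model does not converge in this small sample, use ANCOVA at each visit with baseline and stratum. It keeps nearly all the precision, but baseline adjustment alone left 0.35 to 0.96 points of bias in the unequal-loss simulations.
- Report loss by arm, visit and baseline score.
- State that the model assumes data are missing at random, and that it only reduces bias if loss depends on the unseen T4 score.

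The cost is a short paragraph in the SAP and a few lines of Stata, which the plan already uses. No new data are needed. The added estimate is the same kind of quantity the plan already computes, so it does not turn the pilot into an efficacy analysis.

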## Outcome Measures

Measure Title	Maternal Self-Rating of Depression
Measure Description	Patient-Reported Outcomes Measurement Information System (PROMIS) 8a Higher scores indicate higher levels of depression: T-score: standardized score mean of 50 and standard deviation (SD) of 10
Time Frame	Assessed at Baseline 14 days post-baseline (T2), 28 days post-baseline (T3), and 30 days after infant discharge from the NICU (T4). Change from Baseline to 30 days after infant discharge from the NICU (T4) Reported.
Measure Title	Maternal Self-Rating of Anxiety
Measure Description	Patient-Reported Outcomes Measurement Information System (PROMIS) 8a Higher scores indicate higher levels of anxiety: T-score: standardized score mean of 50 and standard deviation (SD) of 10
Time Frame	Assessed at Baseline, 14 days post-baseline (T2), 28 days post-baseline (T3), and 30 days after infant discharge from the NICU (T4). Change from Baseline to 30 days after infant discharge from the NICU (T4) Reported.
Measure Title	Receipt of Mother's Human Milk
Measure Description	(exclusive, partial, none).
Time Frame	Assessed at Baseline, 14 days post-baseline (T2), 28 days post-baseline (T3). Reported here is 28 days post-baseline (T3).
Measure Title	Z Score of Weight Gain at 36 Weeks Corrected Gestational Age
Measure Description	Z-score method; Z score $\Delta$ weight (g), Birthweight (g) - infant weight (g) at 36 weeks corrected gestational age
Time Frame	Calculated for the date that infant is 36 weeks corrected gestational age
Measure Title	NICU Length of Stay
Measure Description	Days of NICU hospitalization (calculated from days between date of birth to date of discharge from NICU)
Time Frame	Date of NICU discharge will be assessed until study completion, with maximum of 1 year
Measure Title	Infant Hospital Readmissions and Emergency Department Visits Within 30 Days of Infant Discharge.
Measure Description	Coded as Yes/No and extracted from the infant's electronic health record. Mothers were also asked "Did your infant have any re-hospitalizations or emergency department visits within 30 days of discharge?", to ensure all rehospitalizations and ED visits were captured.
Time Frame	Readmissions/ER visits counted within 30 days of discharge will be assessed date of NICU discharge will be assessed until study completion, with maximum of 1 year

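### The SAP's mean-based summaries do not suit receipt of mother's milk, a three-level category with no numeric codes, and no between-arm estimate suited to a category is named (minor)

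*Combined protocol and SAP*

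**What the plan says.** The SAP (Analysis) gives three rules without separating outcomes by type:

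- Within arm: "We will compute means and 95% CIs for changes from baseline (T1 to T2-4) for each outcome by arm".
- Between arms: "At each follow-up (T2-4), we will compute mean differences and 95% CI between arms to evaluate trends in outcomes".
- Graphs: "We will graph trends for all variables over infant Day of Life (DOL) and CGA, comparing boxplots between arms and over time".

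The only other summary it names is generic descriptive statistics. It also says that the pilot will not test for differences or estimate effect sizes, because its main purpose is feasibility.

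The Outcome Measures section lists six outcomes. The two PROMIS T-scores (depression, anxiety) are measured at baseline, T2, T3 and T4. The others differ:

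- Mother's milk has the levels "exclusive, partial, none", with this schedule: "Assessed at Baseline, 14 days post-baseline (T2), 28 days post-baseline (T3). Reported here is 28 days post-baseline (T3".
- The weight z-score is taken once, at 36 weeks corrected age, and is already a change: "Birthweight (g) - infant weight (g) at 36 weeks corrected gestational age".
- Length of stay is one duration: "Days of NICU hospitalization (calculated from days between date of birth to date of discharge from NICU".
- Readmission/ED is one indicator for the 30 days after discharge: "Coded as Yes/No and extracted from the infant's electronic health record".

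**The concern.** A mean needs numbers, and the plan assigns none to the milk categories. Whoever runs the analysis must choose a scoring, and that choice can alter the size and even the sign of the result. Exclusive milk and any milk are also different questions. An averaged score merges them, and a boxplot of three levels shows little.

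The Detailed Description names milk receipt among the outcomes the programme is expected to improve, and the Analysis section says the pilot is to inform a larger trial. A milk contrast with an interval would serve that planning, and the plan does not say which contrast it will be.

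The change-from-baseline wording also reaches three outcomes that have no T1 value on the study schedule. There the question is whether the plan lacks a usable estimate or is merely loosely worded.

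**Working it through.** The plan gives no figure to reproduce on this point. The check matches each outcome to the rules and then asks what a milk mean would measure.

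**1. Fit of the rules** (Outcome Measures against Analysis)

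| Outcome | Scale and timing | Change from T1 | Between-arm mean difference |
|---|---|---|---|
| PROMIS depression | T-score, T1-T4 | fits | fits |
| PROMIS anxiety | T-score, T1-T4 | fits | fits |
| Mother's milk | 3 categories, T1-T3 | needs codes | needs codes |
| Weight z-score | one value, change from birth | does not apply | valid, once |
| Length of stay | one duration | does not apply | valid, once |
| Readmission/ED | one Yes/No | does not apply | valid: a risk difference |

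**2. What a milk score measures.** Score none 0, partial c, exclusive 2. Since P(partial) = P(any) - P(exclusive),

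mean = 2·P(exclusive) + c·P(partial) = (2 - c)·P(exclusive) + c·P(any).

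The between-arm difference is (2 - c)·RD(exclusive) + c·RD(any), where RD is the risk difference. At c = 1 it is the plain sum of the two, so opposite shifts cancel.

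**3. Illustration at one time point.** The documents give no milk proportions, so all counts are assumed. With 30 per arm (SAP, Power) and exclusive/partial/none of 18/3/9 in arm A and 12/15/3 in arm B:

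- c = 1: (36 + 3)/30 = 1.30 and (24 + 15)/30 = 1.30. Difference 0.00, 95% CI -0.41 to 0.41 (pooled t, 58 df).
- c = 0.5: 37.5/30 = 1.25 and 31.5/30 = 1.05. Difference +0.20.
- c = 1.5: 40.5/30 = 1.35 and 46.5/30 = 1.55. Difference -0.20.
- Exclusive: 18/30 against 12/30, +20.0 points (Newcombe -5.0 to +41.8).
- Any: 21/30 against 27/30, -20.0 points (-39.0 to +0.5).

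Study Design gives enrolment as both 44 and 64, or 22 and 32 per arm if split equally. Similar assumed counts behave the same way:

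| Per arm | Counts A; B | Mean, both arms (c = 1) | Exclusive, points | Any, points |
|---|---|---|---|---|
| 22 | 13/2/7; 9/10/3 | 1.27 | +18.2 (-10.6 to +43.1) | -18.2 (-40.9 to +6.9) |
| 32 | 19/3/10; 13/15/4 | 1.28 | +18.8 (-5.5 to +40.1) | -18.8 (-37.6 to +1.7) |

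**4. The same for mean change.** Assume 20/8/2 at baseline in both arms, then 12/16/2 (A) and 16/8/6 (B) at T3, with 30 per arm. The A-minus-B difference in mean change is 0.00 with scores 2/1/0, -0.13 with 1/0/0 (exclusive only), and +0.13 with 1/1/0 (any) or 3/2/0.

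**5. Readmission/ED with few events.** If neither arm had an event, an ordinary mean-difference interval would have zero width. Newcombe gives ±14.9, ±11.4 and ±10.7 points at 22, 30 and 32 per arm. No event rate is stated, so this is a limiting case.

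**6. PROMIS.** With equal variances and baseline-follow-up correlation r, adjusting for baseline multiplies the CI width of an unadjusted follow-up difference by about √(1 - r²). The narrowing, 1 - √(1 - r²), is 5%, 13% and 29% at assumed r of 0.3, 0.5 and 0.7.

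**The case against.** The case for leaving the plan alone has several parts.

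- **Counts will exist.** Descriptive statistics for a three-level variable normally mean counts and percentages. Outcome Measures already fixes T3 as the reported milk time and does not describe milk as a change. Anyone with the T3 counts can derive either risk difference and its interval. This stands: the gap is an unnamed contrast, not lost information.
- **A score is not meaningless.** An equally spaced score is a coarse but interpretable ordinal summary. If exclusive and any milk move the same way, the formula in step 2 gives the same sign for every c between 0 and 2. The illustrations were built to cancel, and nothing in the documents suggests such a pattern. This also stands: they show what a mean can hide, not an expected loss.
- **No T4 for milk.** The T2-4 range reads naturally as the follow-ups at which an outcome is assessed, so the missing T4 is not a defect.
- **Feasibility pilot.** No test or decision depends on milk. Agreed.

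A reader might infer that four of six outcomes have no valid analysis, or that the milk result is unusable. The documents do not support either. Three of the four keep a valid between-arm difference, and milk keeps its counts.

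What the objections do not remove is that the plan applies means to every outcome, states no milk coding, and leaves the choice between exclusive and any milk open until the data are seen.

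**Conclusion.** The point holds, as a minor one. For milk, the mean and mean difference depend on an unstated coding, and no between-arm estimate suited to a category is named. For weight z-score, length of stay and readmission/ED the fault is wording only. The change-from-baseline rule fits the two PROMIS scores as written.

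The table of fit and the identity rest on the documents and algebra alone. The 20-point contrasts, the sign changes and the PROMIS narrowing rest on assumed counts and correlations. All the illustrative risk-difference intervals include zero. No error rate, sample size or decision rule is affected.

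**What to change.** Replace the general rule with one line per outcome type:

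- **PROMIS scores:** keep change from baseline at T2 to T4 for these two only, and adjust between-arm differences for the baseline score already collected.
- **Milk:** report the proportions exclusive and any by arm at T3 (and T2), with risk differences and 95% CIs. Use bar charts instead of boxplots.
- **Readmission/ED:** give one risk difference with a score-type interval such as Newcombe, in case events are few.
- **Weight z-score and length of stay:** give one between-arm mean difference each, with a 95% CI.

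The cost is a few lines of SAP text and routine analysis, with no new data and no change to sample size. There are two downsides. Results will sit on mixed summary scales. And because Study Design already gives actual enrolment and Outcome Measures refers to reported results, any contrast added after enrolment or reporting must be labelled post hoc.

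### The between-arm mean differences and 95% CIs use neither the gestational-age stratum nor the baseline score, and the plan does not say whether they compare raw scores or changes.

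*Combined protocol and SAP*

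**What the plan says.** Under Randomization, the statistician produces a "random allocation sequence stratified by GA at birth (GA <28 weeks and >28 weeks) to balance representation" of the youngest and sickest infants, with "block sizes of 2, 4, and 6 and a 1:1 treatment allocation". The same section says "Research assistants will enroll and collect baseline data before randomization".

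The Analysis section of the SAP then plans two outputs in consecutive sentences. The first is within arm: "We will compute means and 95% CIs for changes from baseline (T1 to T2-4) for each outcome by arm". The second is between arms: "At each follow-up (T2-4), we will compute mean differences and 95% CI between arms to evaluate trends in outcomes". Neither names a regression model, a stratum term or a baseline covariate, and no other section supplies one. The planned graphs over day of life and corrected GA are descriptive.

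For the two PROMIS outcomes, Outcome Measures says "Change from Baseline to 30 days after infant discharge from the NICU (T4) Reported". It does not say how that change is contrasted between arms, and it does not cover T2 or T3.

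The Power and Analysis sections state that the pilot is not powered for between-arm comparisons and that no significance tests will be done.

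**The concern.** Two pieces of pre-randomisation information are collected and then left out of the between-arm estimates.

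- **GA stratum.** Stratified 1:1 allocation makes the arms more alike on GA than simple randomisation would. A two-sample interval that ignores the stratum keeps the GA variation in its error term. If GA is prognostic, the interval is therefore conservative. If it is not, nothing is lost.
- **Baseline score.** Leaving it out keeps the interval valid but usually less precise, whether the difference is raw or in change.

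The undefined contrast adds to this. A chance baseline gap moves the raw difference in one direction and the change difference in the other. Two analysts following the plan could report different PROMIS differences, with different widths, from the same data. The Power section says reliable standard errors and mean differences were lacking beforehand. The pilot's between-arm estimates are a natural source for planning the larger trial, so their definition and precision matter even without a test.

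**Working it through.** The plan states no interval width, so there is no figure of its own to reproduce on this point. The nearby enrolment figure of 72 is 60 × 1.20 and does not enter here.

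**Inputs from the documents.** 30 mothers per arm (Power). SD 10 is the PROMIS T-score reference SD (Outcome Measures), used because no trial SD is given. Allocation is 1:1 in blocks of 2, 4 and 6 within GA stratum (Randomization).

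**Assumed, not in the documents.** Baseline-to-follow-up correlation ρ of 0.3, 0.5 or 0.7, with equal SDs at both times. A 40/60 split between GA strata. A GA gap d of 0, 0.5, 1 or 2 within-stratum SDs.

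**Baseline score: 95% half-widths in T-score points**

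- Raw: t(0.975, 58) × 10 × √(2/30) = 2.002 × 2.582 = 5.17.
- Change: 5.17 × √(2(1 − ρ)).
- Baseline-adjusted: t(0.975, 57) × 10 × √(1 − ρ²) × √(2/30) × √(1 + 1/56). The last factor allows for chance baseline imbalance.

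| ρ | Raw | Change | Adjusted | Adjusted vs raw | Adjusted vs change | Change vs raw |
|---|---|---|---|---|---|---|
| 0.3 | 5.17 | 6.12 | 4.98 | −4% | −19% | +18% |
| 0.5 | 5.17 | 5.17 | 4.52 | −13% | −13% | 0% |
| 0.7 | 5.17 | 4.00 | 3.73 | −28% | −7% | −23% |

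At ρ = 0 the adjusted half-width is 5.22, about 1% wider than raw. Study Design gives actual enrolment as both 44 and 64. With 22 per arm, raw is 6.08 and adjusted runs from 5.88 to 4.40 over ρ = 0.3 to 0.7. With 32 per arm, raw is 5.00 and adjusted 4.81 to 3.60.

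**Chance baseline gap.** Its SE is 10 × √(2/30) = 2.58, so P(|gap| > 3) = 2(1 − Φ(3/2.58)) = 0.245. A gap g shifts the raw difference by ρg and the change difference by −(1 − ρ)g. For g = 3 and ρ from 0.3 to 0.7, that is 0.9 to 2.1 points for raw, or 2.1 to 0.9 points the other way for change.

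**GA stratum.** The share of variance due to stratum is R² = 0.24d²/(1 + 0.24d²), where 0.24 = 0.4 × 0.6. Coverage of the unadjusted interval is 2Φ(1.96/√(1 − R²)) − 1. The narrowing from a stratum term is about 1 − √(1 − R²).

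| d (SD) | R² | Coverage, formula | Coverage, simulated | Narrowing, simulated |
|---|---|---|---|---|
| 0 | 0 | 95.0% | 94.8% | 0% |
| 0.5 | 0.057 | 95.6% | 95.5% | 2.9% |
| 1 | 0.194 | 97.1% | 97.2% | 10.3% |
| 2 | 0.490 | 99.4% | 99.4% | 28.9% |

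The simulation used 20,000 trials per case with N = 60 and the plan's block sizes. The stratum-adjusted interval covered 94.8–95.2%. With no GA effect and ρ from 0 to 0.7, the raw interval covered 94.8–94.9% and the change interval 94.7–95.3%, so omitting baseline costs only precision. A separate simulation with one third of infants in the younger stratum gave the same pattern: unadjusted coverage of about 95/96/98/99% when GA explains 0/10/30/50% of outcome variance.

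**Both terms together.** A simulation of the joint model held about 95% coverage. It cost about 1% in width when nothing was prognostic and narrowed the interval by about 7–36% under the assumed effects. Multiplying the separate factors gives a similar range: 0.963 × 0.971 = 0.935 (ρ = 0.3, d = 0.5) and 0.721 × 0.898 = 0.647 (ρ = 0.7, d = 1).

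**The case against.** This is a feasibility pilot. It plans no tests, disclaims effect-size estimation and makes no power claim. Omitting the stratum is at worst conservative, and omitting baseline leaves coverage intact, so adjustment could be called a preference. A 3-point baseline gap is ordinary sampling variation that the unadjusted interval already allows for. The large gains come from the extreme assumptions: at ρ = 0.3, baseline adjustment saves only 0.19 points (5.17 to 4.98), and the 29% narrowing needs a 2 SD GA gap. Nothing in the documents shows that GA predicts maternal PROMIS scores. The natural reading of a difference at each follow-up is a difference in scores, and Outcome Measures fixes change to T4 as the reported PROMIS result.

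Much of this stands. No bias, type I error or decision rule is at issue, and the gap argument shows that the answer depends on the choice of contrast, not that the intervals fail. The raw-or-change wording alone would be a missing detail. What does not stand is that the omission is immaterial. The plan commits to between-arm differences with CIs despite disclaiming effect sizes, it stratifies on GA to balance the youngest and sickest infants, and the adjustment uses data already held. The plain reading (scores) and the reported PROMIS quantity (change) also point to different contrasts at T4.

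**Conclusion.** The concern holds. The between-arm estimates carry no GA-stratum term and no baseline term, and the PROMIS contrast is not fixed as raw or change. The consequence is lost precision and an ambiguous estimate, not invalid inference. Under the assumed correlations of 0.3 to 0.7, baseline adjustment gives PROMIS intervals 4–28% narrower than raw and 7–19% narrower than change. Choosing change over raw moves the width by +18% to −23%. The stratum term matters only for outcomes related to GA: 3–29% narrower for gaps of 0.5 to 2 SD, with the unadjusted interval covering about 95.5–99%. Length of stay and weight gain are plausible cases, but the documents give no GA effect for any outcome. All sizes rest on the PROMIS reference SD and on the assumed correlation, stratum split and GA effect. The plan should be changed, but no feasibility conclusion depends on it.

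**What to change.** In the Analysis section:

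- For each outcome and timepoint, state whether the between-arm difference is in follow-up values or in change.
- For PROMIS depression and anxiety, estimate the difference and 95% CI from a linear regression on arm, GA stratum as randomised and the T1 T-score, without a hypothesis test.
- If length of stay and weight Z-score are compared between arms, include the GA stratum term only.
- For milk receipt and readmission/ED visits, use a difference in proportions that accounts for GA stratum. Milk receipt has three categories, so say which category or grouping forms the proportion.
- Show the unadjusted estimates alongside.

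Check the stratum boundary against the source file and the REDCap strata. As printed, the strata are below 28 and above 28 weeks, so an eligible infant born at 28 0/7 has none. This may come from the PDF reading. The model should use the boundary actually randomised on.

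The cost is SAP wording and a few lines of Stata. Randomisation and data collection do not change. The model uses two degrees of freedom for PROMIS and one elsewhere, and loses about 1% in width if neither term is prognostic. The document already reports actual enrolment. If estimates have been produced, label each as raw or change and present the adjusted versions as post hoc.
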